#### *Equipment*

There will be a discussion of free VPAP Adapt and H5i units and official transfer of PAP device into participant ownership. Masks and supplies need to be supplied through a DME company and any clarification of insurance can be addressed at this time.

#### *Travel Reimbursement*

Participants will be reimbursed \$80.00 for travel costs during this study. This rate can be prorated for patients who did not complete the study.

#### **Questionnaires:**

**Insomnia Severity Index (ISI):** The seven-item questionnaire asks the individual to rate the level of insomnia and perceptions of sleep problems in the last two weeks. Answers must be provided using a scale from 0-4, with 0 reflecting no problem or being very satisfied to 4 indicating a very severe or very dissatisfied experience. Scores are divided into four tiers: 0-7 equates to no clinically significant insomnia, 8-14 equates to subthreshold insomnia, 15-21 indicates moderate severity insomnia, and 22-28 reflects severe insomnia.

**Epworth Sleepiness Scale (ESS):** The ESS is a simple, self-administered questionnaire which provides a measurement of an individual's general level of daytime sleepiness. The responder is asked on a scale of

0–3 to score the likelihood of falling asleep in eight various situations. A higher score indicates a higher level of sleepiness.

**Functional Outcomes of Sleep (FOSQ-10):** The FOSQ-10 is a shorter version of the FOSQ, an instrument used in both research and clinical practice to assess the impact daytime sleepiness has on daily living activities. Global scores range from 5 to 20; scores less than 15 indicative of severe impairment.

**Visual Analog Scale for Fatigue (VAS-F):** A single question on an 11 point Likert scale evaluating daytime fatigue. Higher scores are indicative of more fatigue.

**Visual Analog Scale for Sleepiness (VAS-S):** A single question on an 11 point Likert scale evaluating daytime sleepiness. Higher scores are indicative of more fatigue.

**Insomnia Impairment Index (III):** The III is an 11 item survey based on research diagnostic criteria for insomnia disorder, which measures forms of daytime impairment in relation to nighttime sleep difficulties. It uses a 5 –point Likert scale and is scored with an inter-item average (0 to 4), with higher scores denoting more impairment.

**Fatigue Severity Scale (FSS):** FSS is a 9 question survey on a 7 point Likert scale evaluating daytime fatigue. Higher scores are indicative of more fatigue.

**Sleep Disorder Breathing (SDB-6):** A 6 item survey assessing frequency (on a 4 point scale) and intensity (on a 4 point scale) of end organ symptoms of SDB including cognitive impairment, morning headache, dry mouth, and nocturia.

**Quality of Life Enjoyment and Satisfaction Questionnaire (QLESQ)-Summary Sheet:** QLESQ is a 17 question survey measuring current life satisfaction. It is an abbreviated version of the full QLESQ and is an expedient and satisfactory substitute for the full version.

**Hopkins Symptom Checklist (HSCL):** This well-known and widely used 25-item inventory measures symptoms of anxiety and depression. Part I of the HSCL has 10 items for anxiety symptoms and Part II of the HSCL has 15 items for depression symptoms. All questions are measured on a four point scale ranging from “Not at all” to “Extremely”.

**Patient Global Assessment of Sleep (PGA):** The PGSA consists of 5 question subjectively assessing daytime and nighttime insomnia symptom improvement (or worsening) on a percent scale in comparison to the intake assessment.

**PAP Units of Distress Survey (PUDS):** The PUDS is a scale of 0-10 measuring current subjective distress as it relates to PAP therapy. This survey is based on the Subjective Units of Distress Scale (SUDS) typically used in a clinical desensitization-based therapy setting to evaluate treatment progress.

**Adverse Effects Checklist (AEC):** This checklist consists of common side effects or adverse experiences common to new PAP users. Symptoms are categorized into three groups: mask problems, pressure problems, or other problems. The checklist will facilitate discussion with the patient at follow-up.

**NOSE-8:** This 8 question survey queries patients on congestion, stuffiness, or runny nose symptoms as they relate to sleep and PAP use on a 5 point Likert scale. This questionnaire also measures subjective treatment efficacy of these symptoms.

**Intake Supplement:** This questionnaire is a baseline assessment of the patient's understanding of the treatment rationale and their views on PAP and sleep medication, so that we can compare any changes in views at the exit interview.

**Exit Interview Questionnaire (EIQ):** This questionnaire is an assessment of the patient's perception of the study including: general overview, treatment rationale, effectiveness of PAP therapy, PAP and sleep medication, long-term treatment of SDB, and PAP devices and masks.

**Sleep Diary:** A sleep diary will be available online for patients to fill out daily. The sleep diary tracks subjective: bed time (BT), sleep onset latency (SOL), wake after sleep onset (WASO), total sleep time (TST), time in bed (TIB), and out of bed time (OOB). They will also complete an 8-item Likert scale for sleep quality ratings in the morning and rate their sleep on a 0-100% scale. The last question will be a rating on our PUDS scale to assess distress or lack thereof in using PAP therapy. Patients will be prompted to indicate if something has changed, such as medications, when they fill out this daily diary.

**Sleep Diary Sleep Quality Rating (8 point Likert scale):** This is a single question on an 8-point Likert Scale (0= extremely good sleep to 7=extremely poor sleep) assessing subjective sleep quality.

**Global Morning Rating of Nightly Sleep:** This is an experimental variable using a global rating system to help us track nightly changes in the sleep experience. In this daily subjective rating scale, 0-100%, 0% reflects an awful night of sleep and 100% reflects a great night of sleep.

**PAP Units of Distress Survey (PUDS):** The PUDS is a scale of 0-10 measuring current subjective distress as it relates to PAP therapy. This survey is based on the Subjective Units of Distress Scale (SUDS) typically used in a clinical desensitization-based therapy setting to evaluate treatment progress.

#### **Polysomnography:**

Polysomnography will be completed at three different time points during the protocol: a diagnostic PSG study is completed during screening (not part of protocol) and three titration PSG studies are completed during the protocol (including a final study completed after four months of treatment with either CPAP or ASV).

PSGs will be conducted by registered sleep technologists at the investigative site. Titration protocols will be followed based on the subject's treatment arm. Scoring criteria will be applied using version 2.0 of the AASM Scoring Manual. PSGs will be scored by the sleep technologist on the night of the study as well as a third party sleep technologist who will be blinded to the treatment mode so as to preserve data integrity.

PSG parameters to be collected include:

- Total sleep time (minutes)
- Total recording time (minutes)
- Sleep efficiency (total sleep time/total recording time)
- Sleep stages (% and minutes of total sleep time): Stage 1, Stage 2, Stage 3, REM
- Awakenings index (arousals/hour)
- Arousal index (arousals/hour)
- Wake after sleep onset (minutes)
- REM consolidation index (total REM time in min/total # of discrete REM periods)
- Apnea-hypopnea index (events/hour)
- Obstructive apnea index (events/hour)
- Central apnea index (events/hour)
- Oxygen desaturation index (events/hour)
- Respiratory effort related arousal (RERA)
- Respiratory disturbance index (RDI)

### **Power Analysis, Sample Size Data Analysis**

#### **Power Analysis and Sample Size:**

Based on our description in the background (see page 6), our work with ASV anticipates an effect size of at least 1.40 to 1.50 change in insomnia severity with ASV PAP therapy. Whereas, based on our clinical experience we presume that the effect of CPAP on insomnia would yield an effect size range between 0.50 and 0.70. Thus, the average net effect between ASV and CPAP use would be ~0.80 effect size. Using a resource specific to clinical research(77)in order to calculate power and sample size estimates, we used a beta of .90 for two tailed significance testing at .05 which arrived at 26 patients per group, or a total sample of 52. Therefore, using the less stringent criteria of beta .80, we believe our sample size allotments of 25 per group or 50 total should prove more than sufficient for this protocol.

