Missing from this body of work is a rigorously designed randomized controlled trial (RCT) of positive airway pressure therapy (PAP-T) for the treatment of chronic insomnia. Such a treatment approach must naturally be conducted if we are to learn how insomnia may or may not be influenced by sleep breathing events. In our own clinical and research experience, we have found that patients with insomnia and comorbid sleep-disordered breathing ("complex insomnia") often demonstrate greater difficulty in tolerating fixed CPAP devices due to the specific problem of expiratory pressure intolerance. Thus, we have progressed toward the use of advanced PAP technology such as auto-bilevel (ABPAP) or adaptive servo-ventilation (ASV) devices in the treatment of these patients, the latter device manifesting

the best results by eliminating expiratory pressure intolerance, central-like pauses or central apneas, any or all of which may arise in patients using fixed CPAP pressures.

Clinically, we have researched two different samples at our center for the value of using advanced devices to treat insomnia patients with sleep apnea. In the first study,(75) we looked at 56 patients who had failed standard PAP therapy and reported anxiety or psychiatric distress associated with use of PAP. While being titrated on standard PAP, all were diagnosed with complex sleep apnea and were subsequently switched to ASV, which resulted in significantly improved sleep efficiency, total REM sleep time, REM consolidation and decreased awakenings, arousals, and time awake during the night. Follow-up on 39 of the 56 patients showed significantly improved adherence indices of nights used and hours per night used compared to standard PAP. Germane to the current protocol, insomnia severity markedly decreased on the Insomnia Severity Index (ISI) (16.8 vs 9.7,  $p = .001$ ,  $d = 1.40$ ). In a more recent study,(76) we looked at follow-up data from 281 patients with moderate to severe insomnia (ISI>15) and diagnosed comorbid OSA or UARS who were using either ASV or ABPAP. We found that regular use (>20hrs per week) of ASV was associated with sizeable decreases in insomnia severity measured on the ISI (19.0 vs 11.9,  $p = .001$ ,  $d = 1.50$ ).

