#### **Data Analysis:**

Primary analysis is a repeated measures ANOVA to test for a group by time interaction with calculated effect sizes (Cohen's d or Hedges g). The initial analysis will be with a single ISI score. Both study completers and intent-to-treat (ITT) analyses will be conducted, albeit this is an efficacy study therefore the ITT is not necessarily germane to the focus of the work.

Several other variables will be analyzed in similar fashion (breathing event indices, sleep consolidation indices, sleep diary metrics, addition secondary variable measurements). As indicated by post-hoc factor analyses, we may also conduct more advanced multi-variate analyses.

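### The ASV effect behind the sample size is not a lower bound for all randomised patients, and 25 per group leaves no reserve for loss at 80% power

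*Combined protocol and SAP*

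**What the plan says.** Power Analysis and Sample Size starts from two pre-post effects. For ASV, "our work with ASV anticipates an effect size of at least 1.40 to 1.50 change in insomnia severity with ASV PAP therapy". For CPAP, "we presume that the effect of CPAP on insomnia would yield an effect size range between 0.50 and 0.70", on the strength of clinical experience. The difference is then taken: "the average net effect between ASV and CPAP use would be ~0.80 effect size". After quoting 26 per group for a stricter target, the section settles on 80% and concludes that "our sample size allotments of 25 per group or 50 total should prove more than sufficient for this protocol". It makes no allowance for drop-out, loss to follow-up or non-use.

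The Background shows where the ASV figures come from. In a series of 56 patients who had failed standard PAP, "Follow-up on 39 of the 56 patients showed significantly improved adherence indices", and the text goes on to report that "insomnia severity markedly decreased on the Insomnia Severity Index (ISI) (16.8 vs 9.7", with d = 1.40. In a second sample, "regular use (>20hrs per week) of ASV was associated with sizeable decreases in insomnia severity" (19.0 to 11.9, d = 1.50).

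Data Analysis states: "Both study completers and intent-to-treat (ITT) analyses will be conducted". It adds that the ITT result matters less because this is an efficacy study.

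**The concern.** An effect seen in patients who returned for follow-up, or who used the device regularly, describes those patients. It may well exceed the average over everyone assigned to the device, so it cannot be called a minimum for a randomised arm. The trial also enrols patients naive to treatment for sleep-disordered breathing (Inclusion criteria, item 6), whereas the 56-patient series had already failed standard PAP.

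The effect and the sample size also need to describe the same people. A user-based effect goes with the number of users analysed. If all randomised patients are analysed, the effect has to reflect non-use. The protocol foresees incomplete participation: Supplemental Follow-up Care speaks of reducing drop-outs, and Travel Reimbursement prorates payment for non-completers.

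What is at stake is how a null group-by-time result would be read. Set against a claim of ample power, it would look like evidence that ASV has no advantage, when the chance of detecting the planned difference may have been well below 80%.

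**Working it through.** **Inputs.** ASV 1.40–1.50, CPAP 0.50–0.70, net about 0.80, two-sided alpha 0.05 and 25 per group (Power Analysis and Sample Size); 39 of 56 followed up (Background). The section's *beta* of .90 and .80 is read as power. Loss and non-use rates are assumptions.

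**Net effect.** Midpoints: 1.45 − 0.60 = 0.85. Extremes: 1.40 − 0.70 = 0.70 and 1.50 − 0.50 = 1.00. The plan uses 0.80.

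**The plan's own figures.** Normal approximation: power = Φ(d√(n/2) − 1.96). With d = 0.80 and n = 25, 0.80 × √12.5 = 2.83; 2.83 − 1.96 = 0.87; Φ(0.87) = 80.7%. The exact two-sample t-test gives 79.1%. So 25 per group reproduces as an 80% design if all 50 patients are analysed and the full 0.80 applies. The 26 per group quoted for 90% does not reproduce: it gives about 81% by the t-test, and 90% needs 34. That is a separate error, but it means the step down from 26 to 25 does not show a margin.

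**Loss and equal non-use, at d = 0.80.** Completers: the effect stays at 0.80 and n = 25 × retention. ITT: n stays at 25 and d = 0.80 × proportion using, assuming no change in non-users, equal non-use in both arms and an unchanged SD.

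| Retention or use | Completers per group | Completer power, t (normal) | ITT d | ITT power, t (normal) |
|---|---|---|---|---|
| 100% | 25 | 79.1% (80.7%) | 0.80 | 79.1% (80.7%) |
| 90% | 22.5 | 74.6% (76.5%) | 0.72 | 70.3% (72.1%) |
| 80% | 20 | 69.3% (71.6%) | 0.64 | 60.2% (61.9%) |
| 70% | 17 | 61.9% (64.5%) | 0.56 | 49.2% (50.8%) |

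The last row uses roughly the follow-up fraction of the cited series (39/56 = 69.6%) and is an illustrative extreme.

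**Unequal non-use, ITT.** With midpoint effects and non-use a (ASV) and c (CPAP), d = 1.45(1 − a) − 0.60(1 − c). Power by t-test, 25 per group:
- a = c = 0: d = 0.85, 83.8%
- a = c = 10%: 1.305 − 0.54 = 0.765, 75.5%
- a = 10%, c = 30%: 1.305 − 0.42 = 0.885, 87%
- a = 20%, c = 30%: 1.16 − 0.42 = 0.74, 73%
- a = 20%, c = 40%: 1.16 − 0.36 = 0.80, 79%
- a = 30%, c = 10%: 1.015 − 0.54 = 0.475, 38%

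These start from 0.85, so they are not directly comparable with the table. They show that the direction of the change depends on which arm has more non-use.

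**Detectable effect at 80% power (t-test).** 0.81 with 25 analysed per group, 0.91 with 20, and about 0.98 with 17–18.

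**The case against.** Several points on the other side carry weight.

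*No trial drop-out rate is given.* This stands. A reader might take 39/56 as the expected retention and infer roughly even odds of success. The documents do not support that: the fraction comes from a case series of patients who had failed PAP and reported distress with it, while this trial has scheduled visits, two re-titrations, PAP-Naps, phone support and a free device on completion.

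*Non-use may favour the ITT contrast.* This stands too. Titration #1 (Initial) expects less intolerance with ASV than with CPAP, and the calculation shows power can then rise. It is also unstated whether the CPAP range of 0.50–0.70 already includes non-users; if it does, diluting it again double-counts.

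*Twenty-five may mean patients analysed.* The Protocol abstract speaks of about 25 per group using a device, and Final Dataset of RCT covers participants in the 14–16 week window. At 5–10 candidates a month over 12–18 months (5 × 12 = 60 to 10 × 18 = 180), enrolling more than 50 is not ruled out. On that reading completer power is 79–81%. No replacement rule is given, so the reading is open but not established.

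*The plan rounded 0.85 down to 0.80.* At 0.85, t-test completer power is 83.8% with no loss, 79.6% at 10%, 74.5% at 20% and 67.1% with 17 per group. This gives some cushion, but the plan's stated effect is 0.80. At the low end of its own range (0.70), 25 per group gives 68% with no loss.

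*Baseline correlation might help.* If d is scaled to the raw SD, a baseline-to-follow-up correlation above 0.5 raises the power of the group-by-time test and one below 0.5 lowers it. The documents give no correlation and sized the trial from a t-test table.

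*The 79% is a near miss.* Agreed. The gap between 79% and 81% is a matter of method. The point is the absence of reserve.

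**Conclusion.** The concern holds in this form. The 1.40–1.50 is linked to a series with partial follow-up and to regular users, so *at least* is unsupported for a randomised arm. The Background implies, but does not state outright, that 1.40 was computed on the 39 patients followed up.

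At the plan's net effect of 0.80, 25 analysed per group just reaches the 80% target. If 25 per group are randomised, any loss takes completer power below 80% by the t-test: about 75% at 10% loss and 69% at 20%, with 62% at 30% as the illustrative extreme. This assumes that 0.80 is the true effect among completers and that the t-test sizing carries over to the group-by-time test.

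A reader might go further and conclude that the design misses its power in both analyses. For ITT that is not established. Equal non-use with no change in non-users gives about 70% at 10% and 60% at 20%, but the result can be better or worse depending on how non-use divides between the arms, which the documents do not quantify.

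**What to change.** Revise the power paragraph as follows:
- Delete *at least* and *more than sufficient*.
- State that 1.40–1.50 is a pre-post effect, from a case series with follow-up on 39 of 56 patients and from users of more than 20 hours a week.
- Say whether 25 per group counts randomised or completing patients.
- Restate the power of the fixed 25 per group for the completer and ITT analyses over an assumed 70–100% retention, with the non-use assumed in each arm written out.
- Give the detectable effects at 80% power calculated above for 25, 20 and 17–18 analysed per group.

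The cost is one reworded paragraph and a less favourable stated power. The correction requires no increase in enrolment and no change to the primary analysis.

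### The 26 per group presented as giving 90% power at an effect size of 0.80 gives about 81%; 90% needs 34 per group, so the chosen 25 per group has no reserve.

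*Combined protocol and SAP*

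**What the plan says.** All of this is in the combined protocol and SAP, under Power Analysis and Sample Size, unless another section is named.

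- **Component effects.** ASV is expected to give "an effect size of at least 1.40 to 1.50 change in insomnia severity with ASV PAP therapy", and CPAP is presumed, from clinical experience, to be an intervention that "would yield an effect size range between 0.50 and 0.70".
- **Net effect.** From these, "the average net effect between ASV and CPAP use would be ~0.80 effect size".
- **Sample size.** On that basis, "we used a beta of .90 for two tailed significance testing at .05 which arrived at 26 patients per group", that is, 52 in total.
- **Step down.** Then, "using the less stringent criteria of beta .80", the plan concludes: "we believe our sample size allotments of 25 per group or 50 total should prove more than sufficient for this protocol".

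The .80 criterion is called less stringent than .90, so the word beta can only mean power here. The source cited for the calculation (reference 77) is, by its title, a table of sample sizes for the t test comparing two means. No dropout rate and no inflation for dropout are given.

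**The concern.** The argument for 25 per group has two steps: 26 gives 90% power, and the trial needs only 80%, so 25 leaves plenty in hand. If 26 is really the 80% figure, the second step fails, because 25 is then at or just below the relaxed criterion with nothing to spare.

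Two things are at stake. The stated power is the justification for the sample size, and it is wrong. And a null result would be read as coming from a trial planned around a 90% figure with a comfortable margin. Under the plan's own effect size the chance of missing a true effect would be about 21% with complete follow-up, and more with any losses.

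**Working it through.** **Inputs, all from the plan.** Effect size d = 0.80; two-sided alpha 0.05; equal groups (two groups of about 25, Protocol abstract); power 0.90, then 0.80; two-sample t test (title of reference 77).

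**1. Trying to reproduce 26 at 90%.** Normal approximation, n per group = 2(z₀.₉₇₅ + z_power)² / d².
- 90%: 2(1.960 + 1.282)² / 0.64 = 32.8, so 33.
- 80%: 2(1.960 + 0.842)² / 0.64 = 24.5, so 25.

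With the noncentral t distribution, which is exact for the t test:
- 90%: 33.8, so **34**.
- 80%: 25.5, so **26**.

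The plan's 26 is exactly the t-test answer for 80% power. It does not reproduce at 90% by either formula.

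**2. Power at the stated sizes, d = 0.80, two-sided 0.05.**

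| n per group | t test | normal approximation |
|---|---|---|
| 25 | 79.1% | 80.7% |
| 26 | 80.7% | 82.2% |
| 33 | 89.3% | 90.1% |
| 34 | 90.2% | 91.0% |

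With a single loss (25 versus 24) the figures are 78.3% and 79.9%. So 25 per group is under 80% from the start by the t test, and falls under it at the first loss by the normal approximation.

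**3. Can another reading rescue 26 at 90%?**
- One-sided 0.05: 26 per group gives 88.5%, still short, and the plan specifies "two tailed significance testing at .05".
- A larger effect: 26 per group reaches 90% only at d = 0.92.
- The plan's component ranges: low end 1.40 − 0.70 = 0.70; high end 1.50 − 0.50 = 1.00; midpoint 1.45 − 0.60 = 0.85. At 0.85, 90% needs 31 per group (30 by the normal approximation). At 1.00, 26 would be more than enough (23 needed), but the plan did not use that value.

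**4. Sensitivity of the chosen 25 per group (t test).** Over the plan's own range, with complete follow-up: d = 0.70, 67.9%; d = 0.80, 79.1%; d = 0.85, 83.8%. The effect detectable with 80% power is 0.81.

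**5. Losses.** The plan gives no rate, so these evaluable numbers are assumptions, at d = 0.80: 22 per group, 73.6%; 20 per group, 69.3%; 17 per group, 61.9%. The last applies the retention in the plan's first ASV series in the Background, "Follow-up on 39 of the 56 patients": 25 × 39/56 = 17.4. The corresponding chances of missing a true effect are about 26%, 31% and 38%.

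Some loss is foreseeable from the plan itself. The dataset for the main paper consists of participants in the 14 to 16 week window (Final Dataset of RCT), and Data Analysis plays down the ITT analysis beside that of completers. The PAP-NAP text anticipates drop-outs. Special Considerations provides for removing some patients on titration findings, and titration comes after randomisation.

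**The case against.** The mislabelled sentence has no defence at an effect of 0.80, but there are fair objections to how much follows from it.

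- **The 90% label is attached to 26, not to the adopted 25.** For 25 the plan invokes .80, and the true figure (79.1% or 80.7%, depending on the formula) is within one point of that. This is correct as far as it goes. But if 26 gave 90%, 25 would give nearly as much, so the claim of ample size does rest on the false figure. What fails is the reserve.
- **At the midpoint effect of 0.85 there is some reserve.** Power is 83.8% at 25 and 80.5% at 23 per group. This stands and should be reported, but the plan bases its calculation on about 0.80.
- **The planned test is a repeated measures ANOVA, not a t test on one score.** If 0.80 is in units of the raw ISI standard deviation and change is tested, the effective size is 0.80 / √(2(1 − r)), where r is the pre-post correlation. The documents give no r. Over an assumed 0.3 to 0.7, power at 25 per group runs from 65% to 95%, with 79% at 0.5. An r somewhat above 0.6 would even bring 26 to 90%. This stands as a caveat on every figure above. It does not make the printed statement right, because the plan makes no such adjustment.
- **The dropout figures are illustrations.** The 39 of 56 comes from patients who had already failed standard PAP, whereas this trial takes treatment-naive patients and offers frequent contact, travel reimbursement and a free device. The ISI is also collected at every follow-up visit, so a dropout is not always a lost observation. Accepted: 62% is not a forecast. The absence of any allowance remains.

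A related point, that the ASV effects are pre-post changes in followed-up or regular users and so do not set a floor, concerns the assumptions and not the arithmetic. The finding does not depend on it.

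**Conclusion.** The concern holds. From the plan's stated inputs, 26 per group gives 80.7% power and not 90%, which would need 34 per group, or 68 in total before any dropout. The adopted 25 per group sits at the 80% boundary with no reserve, and any loss takes it below by either formula. The description of 25 as ample is therefore unsupported at the effect size the plan chose.

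This rests on reading beta as power, which the text forces; on the t test named in the cited source; and on 0.80 being the standardised difference in the quantity tested. The comparison of 26 with 34 needs no assumption about dropout. The figures of 62% to 74% do, and should be labelled as conditional on it.

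This must be corrected, because a wrong power figure is the stated justification for the sample size.

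**What to change.** Rewrite the one paragraph:

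- Use the word power in place of beta. State that 26 per group corresponds to 80% power at d = 0.80, two-sided 0.05, and that 90% would need 34 per group.
- State that 25 per group gives about 79% power at d = 0.80 with complete follow-up, 68% at 0.70 and 84% at 0.85, with a minimum detectable effect of 0.81 at 80% power.
- Add the power under stated losses: for example 74%, 69% and 62% at d = 0.80 with 22, 20 and 17 evaluable per group, marked as assumptions.
- Say whether 0.80 refers to the raw score or to change, and that the figures depend on the pre-post correlation if it refers to the raw score.
- Remove the claim that 25 per group leaves a margin.

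The cost is rewording one paragraph and a less favourable stated power. Enrolment, visits, endpoints and the planned analysis can stay as they are.
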